11.3.1 Replacement Policy

Patients need to take 80% of doses in the one week lead-in and Cycle 1 to be evaluable for DLTs. The 80% completion can be non-consecutive days of dosing with study drug within the one week lead-in and Cycle. If a patient is not considered evaluable for DLTs, they must be replaced for the purposes of dose escalation.

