4.3 Strategies for Recruitment and Retention

Patients will be recruited from the practice of the Medical Oncology Department of the Thomas Jefferson University Hospital. The patients must be 18 years of age or older. Patients who meet eligibility criteria will be invited by their physician to participate in the study. All therapeutic options will be discussed with the patient and the patient's questions will be answered to the

patient's satisfaction. Patients will be asked to read, comment, and ask questions about the study and then sign the informed consent form before study procedures take place.

4.4 **Participant Withdrawal**

4.4.1 **Reasons for Withdrawal**

Patients are free to withdraw from participation in the study at any time upon request.

An investigator may terminate a study patient's participation in the study if:

- Any clinical adverse event (AE), laboratory abnormality, or other medical condition or situation occurs such that continued participation in the study would not be in the best interest of the participant.
- The patient meets an exclusion criterion (either newly developed or not previously recognized) that precludes further study participation.
- The patient does not comply with study medications and procedures
- The physician determines that ongoing participation would be detrimental to the patient
- The patient no longer wishes to participate
- Documented disease progression, unless the investigator (in consultation with the sponsor) deems that continued treatment is appropriate.
- Initiation of a new anti-cancer therapy

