6.2.1 Dose Escalation Procedures

Dose Escalation Schedule										
	Dose*									
Dose Level	Palbociclib (mg)	Dexamethasone (mg)								
Level -1	75	20								
Level 1	100	20								
Level 2	125	20								
Level 3	150	20								
*Doses are stated as exact rather than as a percentag	t dose in units (e.g., mg ge.	g/m², mcg/kg, etc.)								

The dose escalation portion of this study will enroll within each cohort according to a "3+3 design", as explained in the following scheme. Palbociclib will be given as a 1 week lead in alone at the appropriate dose level. This will be followed by 4 weeks of Palbociclib in combination with dexamethasone (induction phase). Patients will receive dexamethasone 20mg daily from days 1-7, 16mg daily from days 8-14, 12mg daily from days 15-21, and 8g daily from days 22-28. Maintenance phase will consist of 1 week of Palbociclib with a dexamethasone 20mg daily followed by 3 weeks of Palbociclib alone. See Section 5.4 for Palbociclib dose modifications/dose levels.

Patients who experience a DLT during the evaluation period as defined below, will stop the study drugs and come off of the trial.

Patients who complete the first cycle of maintenance but require treatment to be held up to 4 weeks to achieve count recovery, will have Palbociclib resumed with a level -1 dose reduction.

The dose escalation portion of this study will follow a traditional 3+3 design, escalating to the next higher dose cohort if 3 patients are treated and no DLTs are observed in the first cycle of therapy. The following will be will be defined as a DLT:

Toxicity	DLT Criteria*								
Hematology	 Marrow aplasia (defined as <10% cellularity with <10% blasts for ≥ 6 weeks not attributable to disease) 								
	 Grade 4 neutropenia persisting ≥6 weeks from the start of a cycle that is not attributable to the underlying disease 								
Cardiac	Any ≥ Grade 3 toxicity								
Gastro-intestinal	Any ≥ Grade 3 toxicity except:								
	 Grade 3 nausea, vomiting**, or diarrhea** not requiring total parenteral nutrition (TPN) or tube-feeding 								
Hepato-biliary	An increase in AST or ALT >3 x ULN and concurrent increase in total bilirubin >2 x ULN (Hy's Law)								
	Any > Grade 3 toxicity except:								
	Any Grade 3 or 4 liver abnormalities (AST. ALT. or alkaline								
	phosphatase) that resolve to < grade 2 within 72 hours								
	 Grade 3 hyperbilirubinemia that resolves to < grade 2 within 72 hours 								

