	 Grade 3 indirect hyperbilirubinemia that resolves to < grade 2 within 72 hours 								
Renal	Any ≥ Grade 3 toxicity								
Non-	≥ Grade 3, including electrolyte abnormalities, except as noted elsewhere in								
Hematologic	the table								
Exceptions to	Grade 3 alopecia								
DLI criteria	Grade 3 fatigue of < 5 days' duration								
	Grade 3 electrolyte abnormalities that last <72 hours								
	 Infection (including neutropenic fever), unless the investigator 								
	determines that the infection or neutropenic fever resulted from the degree or duration of myelosuppression in the absence of persistent								
	ieureillia								

* CTCAE version 5.0 should be used for grading.

** Optimal therapy for vomiting and diarrhea should be based on institutional guidelines with consideration of the prohibited medications listed in these protocol guidelines.

The DLT evaluation period is defined as 35 days (one week lead-in plus Cycle 1). In order to be considered evaluable, the patient needs to take 80% of the doses in the one week lead-in and Cycle 1 (1 cycle=28 days). The 80% completion can be non-consecutive days of dosing with study drug within the one week lead-in and Cycle 1. Any DLT will be followed until resolution.

If one DLT is recorded, then three additional patients will be enrolled into the present cohort. If no further DLTs occur (1 out of 6 DLTs) then the next patient will be enrolled in the next higher cohort. If 2 out of 6 patients have an observed DLT in any given cohort, 3 additional patients will be treated at one dose level lower, and if no additional DLTs are observed, this will be the maximum tolerated dose. If no DLTs are observed in all three cohorts then the expansion phase dose will be cohort 3 for the expansion phase. Toxicities will be graded according to the National Cancer Institute, Common Toxicity Criteria for Adverse Events version 4.0 (NCI CTCAE v5.0). If multiple toxicities are seen, the presence of DLT will be based on the most severe toxicity experience.

Once three patients have enrolled onto the dose cohort and the DLT evaluation period or the third patient has passed, a meeting will be held with the PI and the TJU Medical Monitor to review the safety information. If it is determined safe to open the next dose cohort, a formal letter from the Medical Monitor will be issued. Please see Appendix D for more information.

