** Optimal therapy for vomiting and diarrhea should be based on institutional guidelines with consideration of the prohibited medications listed in these protocol guidelines.

The design is constructed to reduce the chance of escalating the dose when the probability of DLT is high, and increase the chance of escalating the dose when the probability of DLT is low. The maximum tolerated dose (MTD) is defined as the highest dose level where a DLT occurs in at most one out of six patients treated. The escalation scheme is as follows:

(1) If none of the initial three patients in a cohort experiences a DLT, then a new cohort of three patients will be treated at the next higher dose level.

(2) If one of the three patients in a cohort experiences a DLT, then up to three additional patients will be treated at the same dose. Escalation will continue if only one of six patients experiences DLT.

(3) If two or more patients in a cohort experience DLT, then the MTD will have been exceeded, and no further dose escalation will occur. The previous dose level will be considered the MTD.

(4) If only three patients were treated at a dose level under consideration as the MTD, then up to three additional patients will be accrued. If no more than one of the six patients at that dose level experience a DLT, then that dose level will be confirmed as the MTD. If two or more patients in that cohort experience DLT, then the previous dose level will be studied in the same fashion.

The MTD is defined as the highest dose studied for which the observed incidence of DLT is less than 33%. Frequencies of toxicities will be tabulated according to the NCI Common Toxicity Criteria. Patients will be continued to be followed for one year for evidence of late toxicity.

Table 1.1 below gives the probabilities of dose escalation based on true DLT risk in the 3+3 design.

True DLT rate										
		10%	20%	30%	40%	50%	60%	70%	80%	90%
Probability c escalation	of	0.91	0.71	0.49	0.31	0.17	0.08	0.03	0.01	0.001

All patients treated with at least one dose will be included in the safety analysis.

Response criteria for the study are defined as follows:

Response Criteria Complete Remission (CR) No lymphoblasts in the bone marrow Absolute neutrophil count ≥0.75 x10⁹/L Platelet count ≥75 x 10⁹ /L

Complete Remission with Incomplete Hematologic Recovery (CRi)

<5% lymphoblasts in the bone marrow

Partial Remission (PR)

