11.3 Sample Size Considerations

This traditional 3+3 dose escalation study will include a minimum of 4 and a maximum of 24 participants. The minimum sample size of 4 would be achieved if \geq 2 patients out of the first 3 patients have a DLT at dose levels 1 and -1. The maximum sample size of 18 would be achieved if 6 patients are enrolled at dose levels -1 through 3 (100 mg, 125mg, 150mg, 175mg). The anticipated sample size is 12-18.

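### The 80%-of-doses evaluability rule does not exempt a patient who stops because of a DLT; read literally, a DLT before about induction Day 21 is replaced and lost from the 3+3 count

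*Combined protocol and SAP*

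**What the plan says.** Evaluability is defined twice, each time by dose count alone. Section 6.2.1: "In order to be considered evaluable, the patient needs to take 80% of the doses in the one week lead-in and Cycle 1". Section 11.3.1: "Patients need to take 80% of doses in the one week lead-in and Cycle 1 to be evaluable for DLTs". Section 11.3.1 then sets the consequence: "If a patient is not considered evaluable for DLTs, they must be replaced for the purposes of dose escalation". The evaluation window in 6.2.1 is 35 days: the 7-day lead-in plus the 28-day Cycle 1.

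Section 6.2.1 also says what happens after a DLT: "Patients who experience a DLT during the evaluation period as defined below, will stop the study drugs and come off of the trial". Sections 3, 5.4 and 11.2 repeat this.

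The escalation rules in 11.2 are written in terms of patients who have a DLT and do not mention doses taken. Rule (3) reads: "If two or more patients in a cohort experience DLT, then the MTD will have been exceeded, and no further dose escalation will occur". Section 11.3 gives a minimum sample size of 4, reached if at least "2 patients out of the first 3 patients have a DLT at dose levels 1 and -1". Section 11.2 puts every patient who received at least one dose in the safety analysis, but that sentence does not govern the escalation count.

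**The concern.** A DLT ends dosing. A patient whose dosing ends early cannot reach 80% of the planned doses, is therefore not evaluable, and under 11.3.1 must be replaced. The same happens to a patient with a DLT whose dosing ends early for progression under Section 4.4.1. No sentence in the available text makes a patient evaluable because of having had a DLT.

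Followed as written, the replacement rule removes from the escalation count the early DLTs that should halt escalation. DLT and MTD are the primary endpoint (Section 2.2.1). Dropping DLTs can only lower the counted rate, so the MTD can be biased only upward.

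**Working it through.** **1. Reproduce Table 1.1.** With true DLT rate p, the 3+3 rules escalate after 0 of 3, or after 1 of 3 followed by 0 of 3:

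P(escalate) = (1−p)³ + 3p(1−p)² × (1−p)³ = (1−p)³ + 3p(1−p)⁵

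For p = 0.1, 0.2, 0.3, 0.4 this gives 0.906, 0.709, 0.494, 0.309, which agrees with the printed 0.91, 0.71, 0.49, 0.31. The other five entries also reproduce. Table 1.1 therefore assumes that every DLT counts.

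**2. Find the cut-off.** Inputs: 35-day window (6.2.1), one palbociclib dose a day (5.3), lead-in from Day −7 to Day −1 (Section 3).

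- 0.80 × 35 = 28 doses = 7 lead-in + 21 induction.
- Last dose on Day 20: 27/35 = 77.1%, not evaluable.
- Last dose on Day 21: 28/35 = 80.0%, evaluable.
- Counting dexamethasone as well (63 doses in all): (7 + 2×21)/63 = 77.8% on Day 21 and (7 + 2×22)/63 = 51/63 = 81.0% on Day 22.
- Applying 80% to Cycle 1 separately: 0.80 × 28 = 22.4, so 23 doses, reached on Day 23.

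On the palbociclib count, a patient whose last dose falls on any of the first 27 of the 35 days (27/35 = 77% of the window) is below 80%. Missed doses move the cut-off later.

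**3. A worked cohort.** Of three patients, two have a DLT on induction Day 10 and stop with (7 + 10)/35 = 48.6% of doses. The third finishes without a DLT.

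- Rule (3) of 11.2: two DLTs, the MTD is exceeded, escalation stops.
- Section 11.3.1: both are replaced. If both replacements are DLT-free, the cohort reads 0 of 3 and the dose goes up, although 2 of 5 treated patients had a DLT.

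Suppose every later DLT is counted properly. From one DLT-free patient plus two replacements,

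P(escalate) = (1−p)² + 2p(1−p) × (1−p)³

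which is 0.80, 0.63 and 0.46 at p = 0.2, 0.3 and 0.4. Under rule (3) it should be 0.

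**4. Effect on the design.** Let f be the share of DLTs that end dosing before the 80% point. A treated patient has an early DLT with probability pf (replaced), a later DLT with probability p(1−f), and none with probability 1−p. If all DLT-free patients are evaluable and replacement is unlimited, the rate among counted patients is

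p′ = p(1−f)/(1−pf)

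and p′ replaces p in the formula of step 1. The documents give no DLT timing, so f is an assumption; 77% corresponds to uniform onset over the 35 days (27/35).

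| f | p = 0.30: p′ | P(escalate) | p = 0.40: p′ | P(escalate) |
|---|---|---|---|---|
| 0 (Table 1.1) | 0.300 | 0.49 | 0.400 | 0.31 |
| 25% | 0.243 | 0.61 | 0.333 | 0.43 |
| 50% | 0.176 | 0.76 | 0.250 | 0.60 |
| 77% | 0.089 | 0.92 | 0.132 | 0.85 |

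A simulation of 200,000 runs agreed: 0.758 at p = 0.3 with f = 0.5, and 0.600 and 0.849 at p = 0.4 with f = 0.5 and 0.77.

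**5. Check against the minimum sample size.** Four patients means 2 at level 1 plus 2 at level −1, all with a DLT and none replaced. Section 11.3 puts no condition on when those DLTs occur. Under the literal 11.3.1 rule, four would suffice only if all four DLTs came after the 80% point.

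**The case against.** The strongest reply is that the protocol, read as a whole, already counts these DLTs. The escalation rules turn on the event, and the minimum of 4 presupposes that it counts. Evaluable for DLTs can be taken to mean exposed long enough to be called DLT-free. On that view only a clarifying clause is missing. This is probably the intent, and a team following convention would act on it. But 11.3.1 says such a patient must be replaced, and says so specifically for dose escalation. The other sections therefore conflict with it; they do not override it.

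Escalation is also not automatic. The investigator and the Medical Monitor review safety after each cohort, a formal letter opens the next dose, and the DSMC receives the adverse events. The toxicity stays visible, so the probabilities above describe the written algorithm and not the trial as it would be overseen. None of this defines who is counted, however.

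Both hematologic DLTs need at least 6 weeks (42 days), so this rule cannot discard them early. Nor can they be completed inside the 35-day window. The DLTs that can count within the window are mainly the non-hematologic ones, and those are exposed. Uniform onset is still only an assumption, and the 77% row should be read as the top of a range. Unlimited replacement is a simplification too, because enrollment is capped.

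The text of Appendix D, on requesting escalation approval, was not available, so an exemption there cannot be excluded. Progression under Section 4.4.1 is a side issue: a patient with a DLT must stop anyway, and a DLT-free patient who progresses below 80% is properly replaced.

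**Conclusion.** The concern holds: the counting rule is wrong as written and should be corrected. On the available text, a DLT that ends dosing before the 28th of 35 palbociclib doses (before induction Day 21; Day 22 or 23 on other readings of the 80%) makes the patient non-evaluable and subject to mandatory replacement. That contradicts the escalation rules in 11.2 and the sample-size minimum in 11.3.

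The direction is certain: upward for the MTD. The size depends on DLT timing, which the documents do not give. With 25% to 77% of DLTs before the cut-off, the chance of escalating ranges from 0.61 to 0.92 at a true rate of 30%, and from 0.43 to 0.85 at 40%. These figures assume that the rule is applied literally, that replacement is unlimited and that oversight does not intervene. If the team counts every DLT, Table 1.1 stands.

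**What to change.** Put the same two sentences in 6.2.1 and 11.3.1:

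> A patient is evaluable for DLT if he or she has a DLT at any time in the 35-day window, whatever the number of doses taken, or completes at least 80% of doses without a DLT. Only patients who stop below 80% without a DLT are replaced.

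This restores Table 1.1 as printed. It needs no extra patients, since those with a DLT would no longer be replaced. The discretion on progression in 4.4.1 can stay as it is. Optionally, record the date and basis of any progression before the cohort review with the Medical Monitor.

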11.3.2 Accrual Estimates

We estimate that we will be able to complete accrual within 42 months.

11.4 Exploratory Analysis

Analysis of exploratory endpoints will be descriptive with continuous variables summarized using means, medians, standard deviations, and ranges, and categorical variables summarized using frequencies and percentages. The analyses will occur at the conclusion of the trial.

Plasma levels of palbociclib will be determined on days 1 and 8 of induction and changes will be summarized by dose level. Phospho-RB and FOXM1 will be assessed by Western blot at days 1 and 8 of induction. MYB, BCL2, p21, CDK2, cyclin E, S-Phase, Annexin, V/Caspase 3 will be assessed by gene expression profiles (microarray or RNA-Seq) on days 1 and 8 of induction.

12 Source Documents and Access to Source Data/Documents

Study staff will maintain appropriate medical and research records for this study, in compliance with ICH E6, and regulatory and institutional requirements for the protection of confidentiality of participant information. Study staff will permit authorized representatives of SKCC and regulatory agencies to examine (and when required by applicable law, to copy) research records for the purposes of quality assurance reviews, audits, and evaluation of the study safety, progress and data validity.

13 Quality Control and Quality Assurance

Study staff will maintain appropriate medical and research records for this study, in compliance with ICH E6, and regulatory and institutional requirements for the protection of confidentiality of participant information. Study staff will permit authorized representatives of SKCC and regulatory agencies to examine (and when required by applicable law, to copy) research records for the purposes of quality assurance reviews, audits, and evaluation of the study safety, progress and data validity.

Source data is all information, original records of clinical findings, observations, or other activities in a clinical trial necessary for the reconstruction and evaluation of the trial. Source data are contained in source documents. Examples of these original documents, and data records include: hospital records, clinical and office charts, laboratory notes, memoranda, subjects' diaries or evaluation checklists, pharmacy dispensing records, recorded data from automated instruments, copies or transcriptions certified after verification as being accurate and complete, microfiches, photographic negatives, microfilm or magnetic media, x-rays, subject files, and records kept at the pharmacy, at the laboratories, and at medico-technical departments involved in the clinical trial.

The study case report form (CRF) is the primary data collection instrument for the study. All data requested on the CRF must be recorded. All missing data must be explained. If a space on the CRF is left blank because the procedure was not done or the question was not asked, write "N/D". If the item is not applicable to the individual case, write "N/A". All entries should be printed legibly in black ink. If any entry error has been made, to correct such an error, draw a single straight line through the incorrect entry and enter the correct data above it. All such changes must be initialed and dated. DO NOT ERASE OR WHITE OUT ERRORS. For clarification of illegible or uncertain entries, print the clarification above the item, then initial and date it.

14 Ethics/Protection of Human Participants

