1.2 Rationale for the Proposed Study

This study will evaluate the use of palbociclib in conjunction with dexamethasone for the treatment of relapsed or refractory ALL. We will begin giving palbociclib at a dose of 100mg PO daily with escalation in increments of 25mg to a maximum dose of 150mg. Initial Phase I testing of palbociclib in patients with advanced solid tumors revealed a maximum tolerated dose (MTD) of 125mg daily. The primary dose limiting toxicity was bone marrow suppression, an important consideration when treating sold tumors, but an expected, and possible surrogate marker for efficacy, in the treatment of leukemia. Dexamethasone may decrease serum drug levels of palbociclib, so we will begin with a palbociclib dose of 100mg and escalate from there. Dosing regimens in ALL vary; in this study, we propose giving dexamethasone at a starting dose of 20mg daily in conjunction with palbociclib, and then decreasing the dose by 4mg weekly over 4 weeks to minimize side effects.

If the combination of palbociclib and dexamethasone is found to be safe and well-tolerated, we would hope to move forward with a larger, Phase II study.

1.3 **Correlative Studies**

The following correlative studies will be performed in the [name] Laboratory:

- 1. RB phosphorylation (CDK4/6 phosphorylation sites) by Western blot as the primary read-out of palbociclib activity.
- 2. FOXM1 expression by Western blot as the secondary read-out of palbociclib activity (since FOXM1 is a CDK4/6 target)

- 3. RNA isolated from CD19+ cells will be used for gene expression profiles (microarray or RNA-Seq) to measure p21 expression as an indicator of cell cycle activity
- RNA isolated from CD19+ cells will be used for gene expression profiles (microarray or RNA-Seq) to measure S-Phase, Annexin V/Caspase 3 activation as indicators of proliferation and apoptosis
- RNA isolated from CD19+ cells will be used for gene expression profiles (microarray or RNA-Seq) to measure Expression of Myb and Bcl-2 as a read-out of dexamethasone sensitivity

These analyses will be performed on pre-treatment samples (peripheral blood and/or bone marrow) as well as on day +1 (after 1 week of palbociclib alone) and day +8 (after 1 week of combined therapy) of treatment (peripheral blood).

1.4 **Potential Risks and Benefits**

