11.2 Analysis Plans

This aim will consist of a Phase I trial of palbociclib to determine the maximum tolerated dose (MTD) of palbociclib when given in combination with dexamethasone. A standard 3+3 dose escalation design will be employed: three dose levels of palbociclib will be explored (100mg, 125mg, 150mg). Patients will be treated in cohorts of size three to six and the dosage will be escalated if the clinical toxicity is acceptable.

Patients who experience a DLT during the evaluation period as defined in section 6.2.1 will stop the study drugs and come off of the trial.

Patients who complete the first cycle of maintenance but require treatment to be held up to 4 weeks to achieve count recovery, will have palbociclib resumed with a level -1 dose reduction. A dose-limiting toxicity (DLT) is defined in the table below:

Toxicity	DLT Criteria*								
Hematology	 Marrow aplasia (defined as <10% cellularity with <10% blasts for ≥ 6 weeks not attributable to disease) 								
	• Grade 4 neutropenia persisting ≥6 weeks from the start of a cycle that								
	is not attributable to the underlying disease								
Cardiac	Any ≥ Grade 3 toxicity								
Gastro-intestinal	Any ≥ Grade 3 toxicity except:								
	 Grade 3 nausea, vomiting**, or diarrhea** not requiring total parenteral nutrition (TPN) or tube-feeding 								
Hepato-biliary	An increase in AST or ALT >3 x ULN and concurrent increase in total								
	bilirubin >2 x ULN (Hy's Law)								
	Any \geq Grade 3 toxicity except:								
	Any Grade 3 or 4 liver abnormalities (AST, ALT, or alkaline								
	phosphatase) that resolve to < grade 2 within 72 hours								
	 Grade 3 hyperbilirubinemia that resolves to < grade 2 within 72 hours One de 2 in dimensional that resolves to < grade 2 within 72 hours 								
	 Grade 3 indirect hyperbilirubinemia that resolves to < grade 2 within 72 hours 								
	nours								
Renal	Any ≥ Grade 3 toxicity								
Non-	≥ Grade 3, except as noted elsewhere in the table								
Hematologic									
Exceptions to	Grade 3 alopecia								
DLT criteria	 Grade 3 fatigue of < 5 days' duration 								
	 Grade 3 electrolyte abnormalities that last <72 hours 								
	 Infection, unless the investigator determines that the infection resulted 								
	from the degree or duration of myelosuppression in the absence of persistent leukemia								

* CTCAE version 5.0 should be used for grading.

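### Section 11.4 reports the palbociclib level change only by dose level, with no stated scale, pooled estimate or interval, which is too imprecise for a moderate dexamethasone interaction

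*Combined protocol and SAP*

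**What the plan says.** Section 11.4 has palbociclib measured in plasma at Day 1 and Day 8 of induction, and says that "changes will be summarized by dose level". The general rule there is that "Analysis of exploratory endpoints will be descriptive", with "continuous variables summarized using means, medians, standard deviations, and ranges". Neither 11.4 nor any other section names a ratio, a log or geometric summary, an analysis across dose levels, or a confidence interval for this endpoint.

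The numbers available are set by the escalation design. Section 11.2 says "Patients will be treated in cohorts of size three to six", and section 11.3 says "The anticipated sample size is 12-18".

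Section 2.1.3 lists palbociclib pharmacokinetics, alone and combined with dexamethasone, first among the exploratory objectives. Section 1.2 gives the reason for interest: "Dexamethasone may decrease serum drug levels of palbociclib". It then offers this as the reason for starting at 100 mg.

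Sections 6.2 and 7.2.2 place pre-dose samples on Day +1, after a week of palbociclib alone, and on Day +8, after a week of both drugs. Section 6.2.1 gives the same dexamethasone dose on days 1-7 at every palbociclib level.

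**The concern.** The question is proportional and has a direction: by what fraction do palbociclib levels fall once dexamethasone is added? The paired samples suit it well. In a patient whose palbociclib dose does not change, the dose largely cancels from the Day 8/Day 1 ratio, so patients at different levels can contribute to one estimate if they share a similar ratio.

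The planned summary does not use this. It splits 12 to 18 patients into groups of three to six and gives no overall figure. Because the scale is open, the changes could be reported as differences, and those would not combine sensibly. If levels are proportional to dose (an assumption), one common proportional fall is 150/100 = 1.5 times larger in absolute terms at 150 mg than at 100 mg.

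At stake is how well the trial can describe an interaction that its own rationale relies on, and whether the scale is chosen before the data are seen.

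**Working it through.** The plan states no precision, power or sample size for this endpoint, so there is no figure of its own to reproduce.

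**Inputs from the documents:** 3 to 6 patients per level (11.2); 12 to 18 patients in total (11.3); one Day 1 and one Day 8 pre-dose level per patient (6.2, 7.2.2).

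**Assumed:** the SD of the within-patient log(Day 8/Day 1) ratio is not in the documents. I take 0.4 and show 0.2 to 0.6. Every patient is taken to give both samples.

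**Formula:** the 95% limits are the geometric mean ratio divided and multiplied by exp(t(0.975, n-1) × SD/√n).

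| n | t | Factor, SD 0.4 | Factor, SD 0.2 to 0.6 |
|---|---|---|---|
| 3 | 4.303 | exp(4.303 × 0.4/√3) = 2.70 | 1.64 to 4.44 |
| 6 | 2.571 | exp(2.571 × 0.4/√6) = 1.52 | 1.23 to 1.88 |
| 12, pooled | 2.201 | exp(2.201 × 0.4/√12) = 1.29 | 1.14 to 1.46 |
| 18, pooled | 2.110 | exp(2.110 × 0.4/√18) = 1.22 | 1.10 to 1.35 |

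Allowing a separate mean for each of three levels (df = N-3) barely alters the pooled factors at SD 0.4: 1.30 at 12 and 1.22 at 18.

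**An estimated ratio of 0.70 (30% reduction), SD 0.4:**
- n=3: 0.70/2.70 to 0.70 × 2.70 = 0.26 to 1.89
- n=6: 0.46 to 1.06
- n=12: 0.54 to 0.90
- n=18: 0.57 to 0.85

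The by-level intervals include 1 and the pooled ones do not. This depends on the SD. At n=3 the interval includes 1 over the whole assumed range (upper limit 1.15 even at SD 0.2). At n=6 it includes 1 once the SD exceeds ln(1/0.70) × √6/2.571 = 0.34. Pooled n=12 loses the exclusion only near the top of the range (upper limit 1.02 at SD 0.6), and n=18 keeps it (0.94).

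**An estimated ratio of 0.50 (halving):**
- n=6: 0.33 to 0.76 at SD 0.4; the upper limit is 0.94 at SD 0.6
- n=3: 0.19 to 1.35 at SD 0.4; the upper limit is 0.82 at SD 0.2

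**Chance that the interval excludes 1:** with an assumed within-patient CV of 30%, the SD of the log ratio is √(2 × ln(1 + 0.30²)) = 0.415. For a true ratio of 0.70 the chance is 15% at n=3, 40% at n=6, 77% at n=12 and 93% at n=18. At a CV of 40% it is 11%, 26%, 54% and 74%. For a true ratio of 0.50, six patients give 90% at a CV of 30% and 70% at 40%.

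**The case against.** The strongest reply is that the plan is descriptive by design. Section 11.1 tests no hypotheses, the escalation and MTD rules use DLTs only, and the exploratory analyses are run at the end of the trial. No decision hangs on these intervals, and a pooled summary could still be added later. That stands and limits the weight of the point. It does not remove it: an interval is compatible with a descriptive analysis, and naming the scale in advance avoids choosing it after seeing the data.

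Three stronger readings are tempting, and the documents do not support them.
- A reader might infer that the plan uses absolute changes and arithmetic means. Section 11.4 says neither word; a percent change would fit its text, and medians and ranges are planned beside the means. The fair criticism is that the scale is unspecified.
- A reader might infer that within-patient comparison is missing. The samples are paired, so the changes are naturally within-patient.
- A reader might infer that even a large reduction could not be shown. At n=6 an observed halving excludes 1 across the assumed SD range. The inference fits n=3 at SD 0.4 or more.

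There is also a case for display by dose. Pooling needs a similar ratio at each level, and the documents do not show dose-proportional exposure. Section 5.4 describes palbociclib as a time-dependent CYP3A inhibitor, so levels could shift between Day 1 and Day 8 without dexamethasone. A single-arm paired ratio cannot separate the two effects. This stands, and it governs how the estimate is labelled.

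Finally, 12 to 18 complete pairs is the favourable case. Section 11.3 allows as few as 4 patients, where the factor at SD 0.4 is exp(3.182 × 0.4/√4) = 1.89, and missed samples would reduce the number of pairs further.

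**Conclusion.** The concern holds in a limited form. Section 11.4 leaves the scale of the change open and offers only by-level summaries of three to six patients, although the paired samples support one pooled ratio. At the assumed SD of 0.4, pooling narrows the 95% factor from 2.70 (n=3) or 1.52 (n=6) to 1.29 (n=12) or 1.22 (n=18). In practice, a reduction of about 30% is unclear within a level but visible when pooled.

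The size rests on an SD that the documents do not give, on complete pairs, and on a similar ratio across levels. The gain in precision from pooling holds throughout the assumed SD range; whether a particular interval excludes 1 does not. The endpoint is exploratory and the MTD is unaffected, so this is a worthwhile but optional improvement.

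**What to change.** Add to section 11.4:
- State that the change is the within-patient Day 8/Day 1 ratio of pre-dose palbociclib levels, analysed on the log scale.
- Report the geometric mean ratio with a 95% confidence interval, pooled over dose levels and also by level. Use the by-level display to judge whether a common ratio is reasonable.
- Include patients who have both samples and whose palbociclib doses before each sample were taken as assigned according to the pill diary. Skipped doses can distort a trough, and sections 6.2.1 and 11.3.1 count a patient as evaluable for DLT at 80% of doses. State how many pairs are excluded and why.
- Describe the result as the change from palbociclib alone to the combination, not as the effect of dexamethasone by itself.

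The cost is a short paragraph and one table, with no new samples, visits or patients. The small downside is the common-ratio assumption, which the by-level display keeps in view.
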